4.3. Medication management

Medication contraindications will include anti-seizure medications, insulin and oral hypoglycemics, certain hypertension medications (clonidine, and aldomet specifically), cardiovascular medications and the following psychotropic medications: anti-psychotics (first and second generation agents), anti-depressants and mood stabilizers. Psychotropic medications cannot be taken in the previous two weeks, with Prozac (fluoxetine) not being taken within the last 5 weeks prior to receiving any study agents. Participants may only take prn (as needed) benzodiazepines (i.e., lorazepam) up to three days before the session.

Participants will refrain from taking any medications the day of medication dosing session, except prescribed opiate pain medication or over-the-counter non-narcotic pain medication at any time. It will also be necessary to refrain from alcohol the day before, the day of, and the day after each medication dosing session.

Participants must agree to:

- a. Ingest only alcohol-free liquids after 24:00 (midnight) the evening before the Medication Dosing Session
- b. Refrain from the use of any exclusionary medications. Except in the case that the PI prescribes benzodiazepine or zolpidem for insomnia.
- c. Refrain from use caffeine or nicotine for two hours before and six hours after ingesting the drug, or until research staff deem it safe to do so.

4.4. Strategies for Recruitment and Retention

Participants will be recruited through social media and professional organizations (i.e., Northwest Healthcare Response Network—the organization that has coordinated the clinician response to the COVID pandemic in Washington state). Because eligible participants will be physicians and nurses, we anticipate a general familiarity with clinical trials, although not for a trial involving PAP. An informational website will be created to enable potential participants to understand the study purpose, inclusion criteria, exclusion criteria, and study email and phone number.

4.5. Participant Withdrawal or Termination

Participants may withdraw their consent for use of their data and/or terminate participation in the study at any moment during the study by calling the Principal Investigator or a member of the research team. To revoke authorization of the use and disclosure of Personal Health Information, the participant must follow-up the phone call by submitting a request in writing to the Principal Investigator. In this event, the Principal Investigator will indicate in the data base that consent from the participant is no longer active, and that data can no longer be used.

Page 24 Version 1.16, July 18, 2022

A participant may be withdrawn from the research for any of the following reasons:

- (1) A participant will be withdrawn if they become actively suicidal
- (2) A participant will be withdrawn if during the preparation visits, they show signs of severe personality disorder that was not evident in the screening visit.
- (3) A participant may be withdrawn if their withdrawal is in the best interests of either the participant or of the research (e.g., due to a medical condition making the procedures unsafe or any condition making interpretation of the results difficult).
- (4) A participant may be withdrawn if they are unable to comply with study visits (e.g., they miss their preparation visits without explanation).

4.6. Premature Termination or Suspension of Study

The Principal Investigator is responsible for monitoring the data, assuring protocol compliance, and conducting quarterly safety reviews. During the review process the principal investigator will evaluate whether the study should continue unchanged, require modification/amendment, or close to enrollment. Likewise, the principal investigator will periodically review the collection, storage, and distribution practices associated with clinical data bank, and determine whether changes to enhance confidentiality and privacy are required.

The Principal Investigator, the Medical Monitor and the IRB have the authority to stop or suspend the study or require modifications.

5. Study Agent

Synthesized psilocybin, the study drug, is a 4-hydroxy-N,N-dimethyltryptamine and occurs in nature in many species of mushrooms, including the genera Psilocybe, Conocybe, Gymnopilus, Panaeolus, and Strophparia. Its chemical formula is $C_{12}H_{17}N_2O_4P$. Psilocybin is a potent agonist at 5-HT2A/C, and their binding potency to these receptors correlates with human potency as hallucinogens [7]. Psilocybin has been administered to normal volunteers to measure physiological and psychological parameters at doses ranging from 0.045mg/kg to 0.43mg/kg [45; 51]. It has also been safely administered to patients with OCD at doses ranging from 0.025mg/kg to 0.3mg/kg.

After the FDA has approved the content of the protocol, the psilocybin will be provided by the Usona Institute, Inc., [name], who will provide this iforefinas a supplement to this IND application. The Usona Institute utilizes a contract manufacturing organization (CMO) to manufacture GMP psilocybin, and the CMO is Almac Pharma Services Limited, [name]. Using a 222 DEA form, the psilocybin will be shipped to [name] to be stored in DEA safe located in the Investigational Pharmacy at Harborview Medical Center. To safeguard the psilocybin, a special storage safe will be approved by DEA to store only the psilocybin. Designated staff will be the only personnel with access to the psilocybin. Both the active and placebo will be prepared by designated study staff by a compounding process. The UW Investigational Pharmacy (IDS) will store and track the accountability of the psilocybin. A log of the psilocybin accountability, compounding, and release to the study team will be kept by the designated IDS staff. This will provide strict safeguarding and accounting of the agent both for internal and external regulatory agencies. The sponsor-investigator will be the DEA Schedule 1 license holder and will dispense the drug directly to study participants.

6. Study Procedure and Schedule

This study will use a randomized, placebo-controlled, double-blind design to examine the clinical and neural effects of psilocybin-assisted psychotherapy with either synthesized psilocybin (25 mg) or placebo (niacin 100 mg), given along with non-drug preparatory and integrative psychotherapy sessions. The duration of the randomized study phase is from consent until two weeks after drug administration, which is approximately 6 weeks. The blind will be broken at 4 weeks after measures have been completed, and the participants who received placebo will be offered the option toreceive open-label psilocybin. In addition to the baseline assessments and medical evaluation, the study will consist of atleast two Preparation sessions with the study therapists, the medication dosing session (which will require at least 7 hours), and post-medication session Integration sessions, starting the following morning after the medication dosing session and continuing at 2 weeks, 3 weeks, and 4 weeks post-medication. These integration sessions may be conducted by secure videoconference.

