Psilocybin will be used in a proven pre- and post-dose psychotherapeutic process defined by prior research conducted by Griffiths and [name]. ^{19,23} In these studies, psychotherapy involved 2 trained therapists for each study participant, and included Preparation sessions conducted in for 6-8 hours total (in 3 sessions) prior to a Psilocybin Dose session, followed by Integration sessions for 6-8 hours (again in 3 sessions). These studies reported a few toxicities, and no severe adverse events. This psychotherapeutic context of Preparation/Psilocybin Dose/Integration was extremely well tolerated and resulted in improvements in anxiety, depressive symptoms, and existential distress that were statistically significant and clinically meaningful. Cancer patients who participated in the Griffith and [name] studies described in qualitative interviews how their existential issues came to have different meanings after their participation in the study in ways that allowed them to cope better, face death with less fear, and experience better quality of life. ²⁴ Because this proposal involves psychedelic-assisted psychotherapy with a new indication and new target population for psychedelic-assisted psychotherapy, the scientific approach most likely to yield valuable results would use a psychotherapeutic process that has been proven.

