3.1. Research Procedures

Participants will complete self-report and clinician-administered measures at baseline, prior to the medication dosing session, and at designated study visits (see figure next page).

Schedule for Activities during Randomized Phase									
Purpose	Screen	Prep	Prep	Medi- cation	Inte- gration	Inte- gration	Inte- gation	Follow -up	
Study day (approx)	-21-14	-7	-1	0	1	8	15	28	
Visit number		V1	V2	V3	V4	V5	V6	V7	
Research activity									
Demographics	X								
Eligibility Determination	X								
Medical exam	X								
Informed consent	X								
Caregiver contact info	X								
Blood draw	X								
Pregnancy screen (if applicable)	X			Х					
PI review of inclusion/exclusion	Х								

Page 18 Version 1.16, July 18, 2022

Informed Consent		X						
Mental health evaluation		Х						
Education re expectations	Х	Х						
Preparation psychotherapy		Х						
Urine screen	Χ							
Randomization				Х				
Medication (psilocybin or control)				Х				
Medication dosing monitoring				Х				
Integration psychotherapy					Х	Х	Х	
Adverse event reporting				Х	Х	Х	Х	
Un-blinding								X**
Measures								
Mont-Asberg Depression (MADRS)	Х	Х			Х	Х		Х
Beck Depression Scale		Х			X	Х		Х
Stanford Fulfillment Index		Х			X	Х		Х
Post-traumatic stress (PCL5)		Х			Х	Х		Х
Likelihood to leave job		Х			Х	Х		Х
Self-reported mystical exp				Х				
Moral injury symptom scale		Х						Х
Psychedelic Music Questionnaire					Х			
Psychological flexibility (AAQII)		Х				Х		Х
Interoceptive awareness (MAIA2)		Х			Х	Х		Х
Suicidality (C-SSRS)	Х	Х	Х	Х	Х	Х	Х	Х
Qualitative interview								Х
Adverse events, Suicidality	Х	Х	Χ	Х	X	Х	Х	Х

^{**}The unblinding will be done after the study coordinator has verified that the Day 28 measures have been completed.

Follow up measures for participants randomized to psilocybin							
Durance	Follow	Follow	Follow				
Purpose	-up	-up	-up				
Study day (approx.)	56	84	180				
Visit number	V8	V9	V10				
Measures							
Mont-Asberg Depression (MADRS)	Х	Х	Х				
Beck Depression Scale	Х	Х	Х				
Stanford Fulfillment Index	Χ	Х	Х				
Post-traumatic stress (PCL5)	Χ	Х	Х				
Likelihood to leave job	Χ	Х	Х				
Psychological flexibility (AAQII)	Χ	Х	X				
Interoceptive awareness (MAIA2)	Χ	Х	X				
Suicidality (C-SSRS)	Χ	X	X				
Qualitative interview							
Adverse events	Χ	Х	X				

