6.2.4. Integration sessions (Visit 4, 5, and 6)

During the meetings with the study therapists after the medication dosing session, participants will complete questionnaire assessment measures. During visit 4, study therapists will also complete questionnaires retrospectively rating various behaviors and experiences observed on the session day and reported by the participant during the meeting (using the Next-Day Monitor Rating Form), and participants will be asked to discuss the narrative description of their medication session.

The purpose of the integration sessions is to ensure psychological stability after the medication dosing session and provide an opportunity for the participant to discuss thoughts or feelings from the session. These post-medication integration sessions allow time for reflection, meaning-making and psychological change. Audio or video recordings (with coded id number) of this session will be made.

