Schedule for Activities during Open Label Psilocybin Phase										
Purpose	Prep	Medi- cation	Inte- gration	Inte- gration	Inte- gation	1 011011	Follow -up	Follow -up	Follow -up	Follow -up
Study day ('denotes open-label)	-1'	0'	1'	7'	14'	21'	28'	56'	84'	180'
Visit number	V7	V8	V9	V10	V11	V12	V13*	V14*	V15*	V16*
Research activity										
Psychiatric evaluation	Х									
Education re expectations	Х									
Preparation psychotherapy	Х									
Urine screen		Х								
Medication (psilocybin)		Х								
Medication dosing monitoring		Х								
Integration psychotherapy			Х	Х	Х					
Adverse event reporting		Х	X	X	X					
Measures										
Montgomery Asberg Depression	Х		Х	Х	Х	Х	Х	Х	X	
Beck Depression Scale	Х		Х	Х	Х	Х	Х	Х	X	
Stanford Fulfillment Index	Х		X	Х	Х	Х	Х	Х	Χ	
Post-traumatic stress (PCL5)	Х		Х	Х	Х	X	X	X	X	

Page 30 Version 1.16, July 18, 2022

Likelihood to leave job	Х				X					
Self-reported mystical exp		X								
Moral injury symptom scale		X						X		
Psychedelic music questionnaire			X							
Psychological flexibility (AAQII)	Χ				X	X	X	X	X	
Suicidality (C-SSRS)	Χ	X	X	X	X	X	X	X	X	X
Qualitative interview						X				
Adverse events	Х	X	X	X	X	X	X	X	X	

^{*}Note that V13, V14, V15, and V16 are likely to be video or remote visits.

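### Section 6 gives four integration sessions up to week 4, the visit table gives three up to Day 15, and no C-SSRS is named between Day 15 and Day 28

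*Combined protocol and SAP*

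**What the plan says.** The opening paragraph of section 6 (Study Procedure and Schedule) has integration sessions beginning the morning after dosing and "continuing at 2 weeks, 3 weeks, and 4 weeks post-medication". The same paragraph says "The duration of the randomized study phase is from consent until two weeks after drug administration" and puts that at roughly 6 weeks. Its next sentence says "The blind will be broken at 4 weeks after measures have been completed".

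The table "Schedule for Activities during Randomized Phase" in section 3.1 marks integration psychotherapy at V4, V5 and V6 (about Days 1, 8 and 15). V7 (Day 28) is a follow-up visit with no integration mark, and there is no column between Day 15 and Day 28. Section 6.2.4 is headed "Integration sessions (Visit 4, 5, and 6", again three visits. In section 6.3, the table "Schedule for Activities during Open Label Psilocybin Phase" has three sessions (Days 1', 7', 14'). Section 1.2 describes the source studies' dosing session as "followed by Integration sessions for 6-8 hours (again in 3 sessions".

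On suicidality, section 1.3.3.8 attaches the Columbia screen to preparation, medication days, integration sessions and follow-up measurements. Section 6.5 attaches it to study visits. In the section 3.1 table, the C-SSRS row and the row "Adverse events, Suicidality" are marked only in visit columns. Section 1.3.3.8 also provides weekly well-being calls, and section 8.2 a weekly adverse-event review up to week 4. Neither mentions the C-SSRS.

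**The concern.** Psychotherapy is part of the intervention in both arms. A therapist following section 6 and one following the visit table would deliver it on different days and possibly in different amounts before the primary MADRS. Section 6 puts its fourth session at week 4, when that MADRS is taken, and does not say which comes first. Section 6.2.6 lets timing vary but requires substantial departures to be reported as deviations, which cannot be judged against two schedules.

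The second issue is participant safety. Under the table, the last two weeks before the primary endpoint contain no scheduled C-SSRS. Participants entered with a MADRS of at least 21 and symptoms that had persisted despite treatment (section 4.1). Those previously treated must stay off antidepressants until the Day-28 measures are done (section 3.1.4), unless withdrawn. Half will have received niacin. The notification step for suicidality in section 1.3.3.8 is triggered by a measured increase, and the table schedules no measurement in this interval.

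**Working it through.** There is no published figure to reproduce. The check counts sessions and days, all of them nominal.

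**Integration sessions**

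| Source | Days | Count |
|---|---|---|
| Section 6 | about 1, 14, 21, 28 | 1 + 3 = 4 |
| Section 3.1 table and 6.2.4 | 1, 8, 15 | 3 |
| Open-label table, 6.3 | 1', 7', 14' | 3 |
| Source studies, 1.2 | not given | 3 |

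Only Day 1 and about Day 14/15 match between section 6 and the visit table. Reading section 6's weeks 2 and 3 as the second and third week (Days 8 and 15) does not reconcile them, because the table still has no integration session at Day 28. If section 6's week-4 session precedes the MADRS, four sessions come before the primary rating; if it follows, three do, on different days from the table's. The difference is at most (4 − 3) × 36 = 36 sessions, with 36 enrolled from section 9.2.

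**Length of the randomized phase**

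- Consent at screening, Day −21 to −14 (section 3.1 table).
- To Day 28: 28 + 14 = 42 to 28 + 21 = 49 days, or 6 to 7 weeks.
- To Day 14: 14 + 14 = 28 to 14 + 21 = 35 days, or 4 to 5 weeks.

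The 6 weeks stated in section 6 fits an end at Day 28, so the two-week wording appears to be the slip. Sections 2.2, 3.1.4 and 6.1 also place unblinding after the 4-week measures.

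**Intervals between named C-SSRS, from dosing to Day 28**

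| Schedule | Days | Gaps (days) | Longest |
|---|---|---|---|
| Section 3.1 table | 0, 1, 8, 15, 28 | 1, 7, 7, 13 | 13 |
| Same, plus Day 21 | 0, 1, 8, 15, 21, 28 | 1, 7, 7, 6, 7 | 7 |
| Section 6 sessions plus the 1-week measures | 0, 1, 8, 14, 21, 28 | 1, 7, 6, 7, 7 | 7 |
| Open-label table | 0', 1', 7', 14', 21', 28' | 1, 6, 7, 7, 7 | 7 |

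The third row includes Day 8 because the 1-week MADRS and PCL5 are required separately (sections 2.3.2 and 9.2). Section 6's own schedule therefore need not leave a gap; the 13 days arise when the visit table governs.

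**What the plan does in similar periods**

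A weekly C-SSRS is named during the antidepressant taper (section 1.3.3.3) and during the wait for open-label dosing (section 1.3.3.8). The open-label table has one at Day 21', although sections 6.1 and 6.3 say that phase follows the randomized phase's schedule of measures.

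**The case against.** The strongest reply is that the session count and phase length are drafting slips in one introductory paragraph. Every other source gives three sessions and unblinding at 4 weeks, and any extra session would fall equally on both arms. This is right about the effect on the comparison. It does not settle what is delivered, because section 6 is operative text.

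On the C-SSRS, the case is that the gap is inferred from silence. Section 1.3.3.3 says the taper calls are not study visits and so are left out of the section 3.1 flowsheets; the table may omit other phone screens too. Section 1.3.3.8 also refers to a therapist manual covering every contact, which is not available here. These points stand as reasons for caution, and the manual should be checked. But the taper C-SSRS is named in the text, whereas no text names one for a call between Day 15 and Day 28. The same remark shows that a phone call is not automatically a study visit under section 6.5.

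Existing safeguards are substantial: at least weekly contact, adverse-event review, a contact adult, an immediately available psychiatrist, and withdrawal on decline or active suicidality. Participants are not unmonitored.

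Finally, the plan sets no 7-day C-SSRS rule for everyone. Screening to V1 is itself 7 to 14 days, and follow-up after Day 28 is sparser still. The taper and the open-label wait differ from Days 15 to 28, and not every participant was on antidepressants. That is fair: preferring 7 days is a judgement, drawn from the plan's own weekly practice in other periods off medication.

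**Conclusion.** The concern holds in all its parts. Section 6 conflicts with the visit table and section 6.2.4 on the number and timing of integration sessions (4 against 3), and with its own next sentence on when the randomized phase ends. If the visit table governs, the longest interval between named C-SSRS assessments from dosing to Day 28 is 13 days.

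The size is modest: one integration session per participant, and one missing named instrument on one weekly call. Sample size, alpha, power, blinding and the Day-28 comparison do not change. The safety part assumes that the therapist manual does not already place a C-SSRS on the weekly calls; if it does, the protocol should say so. The correction should be made, because it settles what is delivered and strengthens suicidality screening at very little cost.

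**What to change.** - In section 6, state three integration sessions at about Days 1, 8 and 15 (V4 to V6), and a randomized phase that ends at Day 28 once the primary measures are complete.
- Add a C-SSRS to the existing weekly call at about Day 21 in both arms, matching Day 21' of the open-label table, and mark it in the section 3.1 table.

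The cost is protocol wording plus one short phone C-SSRS per participant, at most 36, on calls the plan already makes. No extra visit is needed.

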6.1. Randomization Blinded Study Phase

Upon completion of the Preparation sessions, participants will be assigned to one of the two conditions for the Medication Dosing session: the experimental condition (synthesized psilocybin 25mg) or placebo (niacin). The randomization will be performed by IDS and capsules will be placed in envelopes for each participant. Randomization will be stratified by profession (physician vs nurse) and ethnicity (Black or Hispanic vs other).

Psilocybin and niacin will be administered in identically appearing opaque, size 0 gelatin capsule with approximately 180ml of water. The dose of psilocybin will be 25 mg and the niacin will be 100 mg. Each participant will have the option of participating in the medication dosing sessions. In the study, half of the participants will be randomized to receive psilocybin (n=15) or the placebo, niacin (n=15). Following the first treatment session of either the active agent or placebo, participants who were randomized to receive placebo will be offered the option to receive open-label psilocybin. (The blind will be broken at 4weeks to make this determination, after primary endpoint measures have been collected. Clinical raters will remain blind to the treatment assignment). Data will be collected from all subjects after open-label treatment for descriptive purposes, but these data will not be analyzed as part of our primary analysis plan.

The participant's condition assignment will be maintained from randomization until the 4 week unblinding. If there is an adverse event or other emergency requiring knowledge of participant's condition assignment, as when pharmacological intervention is necessary, the blind may be broken for an individual participant. In this case, the study raters who will administer the questionnaires will remain blind to the participant's condition assignment.

Participants in the placebo condition will be eligible for an open-label study continuation. They will be re-screened after the blind is broken to make sure they still meet study criteria. If they are eligible and choose to enroll in the open-label continuation, they may do so, undergoing psilocybin-assisted sessions occurring within another seven to 14-day period.

The open-label phase of the study will follow nearly identical procedures to those used in the randomized phase. Participants will be re-assessed on all study measures following the same schedule of the randomized phase. Participants need not complete any portion of the open-label phase or the several follow up phases for their participation in the study to be considered completed.

6.2. Study schedule for participants by visit

6.2.1. Screening and Informed consent

Prior to participation in this research, subjects will receive a brief secure online screening survey and then if eligible, will be screened by phone to determine preliminary eligibility. All subjects will be informed about the phone screening and what the screening process involves.

All potential participants will be told that we collect demographic information, relevant medical history, and psychiatric history during the screening process. Screening data are entered directly into a secure online database and are considered a source document.

All seemingly eligible subjects will be told that they need to come in for baseline screening visit, and will be informed about baseline questionnaires, clinician assessment, blood draw, and pregnancy test (if applicable) to ensure their eligibility. Subjects are free to decline participation at this point or to discontinue participation at any future point and to withdraw from consideration.

Some potential participants live in another state, and it may not be feasible to have them come for an in-person screening visit. In this case we will conduct the screening interview uligescure video communication platforms. We will ask these participants to send us their most recent physical, and blood work (recent as of 1 month from the screening visit will be allowed). This will be faxed to the PI and reviewed for potential participation. A remote urine test will be ordered for the screening process of remote participants.

Prior to obtaining informed consent, the PI will confirm that the participant meets all study inclusion and exclusion criteria. The investigator or research staff member obtaining consent will ask the participant to provide a brief summary of the study to ensure they understand what is being asked of them and any potential risks and benefits.

Note that if a female subject is pregnant, or breast-feeding, or does not agree to use an approved birth control method (i.e., oral, injectable, or implant birth control, condom, diaphragm with spermicide, intrauterine device, tubal ligation, abstinence, or partner with vasectomy) she will be excluded.

Findings of pregnancy, active cardiac medical issues, abnormal liver function, abnormal renal function, or abnormal blood counts, and any lab indicating an undiagnosed illness would exclude a participant from moving on to the preparation 1 visit. When screening requirements have been met, participants will have a visit with the PI and/or key study personnel in which the study, the scheduling and the procedures will be reviewed. All participants' questions will be answered prior to obtaining an informed consent.

After providing informed consent, the participant will complete initial measures. Note that randomization to the psilocybin or control (niacin) treatment groups will occur at the end of visit 2.

